Four fatal cases have been reported, however, none of the fatal events were assessed by the investigator as related to efgartigimod treatment. Causes of death was unknown in a patient who died at home without witness. The other 3 patients died due to myasthenia gravis crisis, lung cancer Stage IV, and acute myocardial infarction. These 4 patients were between 55 and 79 years old and all had clear comorbidities, including underlying gMG.

Adverse drug reactions were identified based on safety data from the phase 3 double-blind, placebo-controlled trial in patients with gMG and include upper respiratory tract infection, urinary tract infection, bronchitis, myalgia, and procedural headache.

Due to the efgartigimod mechanism of action of reducing IgG levels, AEs in the Infections and Infestations SOC have been defined as AESIs. In the Phase 3 trials with efgartigimod IV in patients with gMG, the most frequently reported treatment-emergent AESIs by preferred term

(PT) were nasopharyngitis, upper respiratory tract infection, urinary tract infection, and bronchitis. Most AESIs were mild or moderate in severity. Few patients had severe or serious AESIs reported, and no SAEs of AESIs were assessed by the investigator as related to efgartigimod treatment.

All therapeutic proteins have the potential to elicit immune responses, potentially resulting in hypersensitivity or allergic reactions. As with any IV injection, the potential exists for infusion-related reactions (IRRs) to occur during or within 48 hours following the administration of efgartigimod. Overall, the frequency of IRRs in the clinical trials was low. At the PT level, no TEAEs of drug hypersensitivity or anaphylactic reaction were reported. None of the IRRs reported were serious. Most IRRs were mild in severity and no IRRs resulted in a change in efgartigimod administration. For administration of efgartigimod PH20 SC, the local injection site will be monitored during the trial.

In the Phase 3 trial with efgartigimod IV in patients with gMG, no differences or imbalances were observed between the efgartigimod and placebo groups in the incidence or rates of abnormal values in clinical laboratory parameters. There was no reduction in levels of serum albumin with the administration of efgartigimod. In the extension trial in patients with gMG, the most frequently reported grade ≥ 3 abnormalities were lymphocyte count decreased.

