The assessments identified for telephone assessment visits are highlighted with the use of bold italics in the existing Schedule of Assessments for Part A in [Table 1](#) and for Part B in [Table 2](#). Guidance on the execution of these visits and assessments is given below.

By providing a structured back-up plan, we aim to mitigate the risks of the COVID-19 pandemic, while still respecting both patient safety and collection of safety data and remaining compliant with GCP.

Visits with the possibility of remote assessment by telephone:

TP_xV2, TPE_xV2, TP_xV3, TPE_xV3, TP_xV4, TPE_xV4, ITP_xV_x, ITPE_xV_x, EoA, EoS, ED, and UNS. See the Schedule of Assessments for Part A ([Table 1](#)) and for Part B ([Table 2](#)).

Treatment Period visits will be replaced by telephone assessment visits during the current COVID-19 situation when the Treatment Period is considered interrupted.

Mandatory physical visits:

Initiating a new Treatment Period can only be done when the patient is physically on site.

Guidance to Sites in Case of Suspected COVID-19 in Patients

As sponsor we want to emphasize and highlight the need to follow the guidance issued by local authorities. Wherever guidance is unclear, or if no specific guidance is available, argenx will recommend to either postpone the visit if possible or evaluate the need for telephone assessments to replace a physical visit.

The site should contact the patient prior to each visit, and conduct the following COVID-19 assessments:

1. Does the patient have symptoms, such as cough, fever, muscle pain, shortness of breath*?

- If NO: Go to Questions 2 and 3.

- If YES:

- The patient should be tested for COVID-19:

The investigator needs to document a positive COVID-19 test as an AESI. The anonymized result needs to be sent to the sponsor for filing. If COVID-19 safety measures are stopped according to local regulations, COVID-19 tests should continue to be performed and the results sent to the sponsor.

*Shortness of breath includes an otherwise unexplained deterioration in the patient's MG-ADL score for breathing. In cases where the MG-ADL score for breathing is 2 or 3 additional COVID-19 testing should be carried out. The exception to this is when a patient has an MG-ADL score for breathing of 2 at baseline. In such cases the patient should only be tested when the MG-ADL score for breathing returns to 2 after previous improvement or when it deteriorates to 3.

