7.2.1.1. Adverse Events of Special Interest

An AESI (serious or non-serious, related or not related) is an event of scientific and medical concern specific to the sponsor’s product or program.

Efgartigimod treatment induces reductions in IgG levels, and there is a potential risk for infections associated with the low IgG levels. As such, any infection will be considered AESI in this trial. Further characterizing information will be collected in the eCRF, such as: location of infection, relationship to underlying condition, medical history and concomitant medication, reoccurrence of previous infection, previous rescue therapy, any confirmatory procedure, culture or urgent medical intervention.

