7.2.1.2. Reporting of Adverse Events and Serious Adverse Events

All AEs that occur during the trial from signature of the ICF until the last study visit are to be recorded on the appropriate AE pages (either “serious” or “non-serious”) in the eCRF. The

investigator should complete all the details requested, including dates of onset, time of onset, stop date (when applicable), stop time (when applicable), severity, action taken, outcome, and relationship to efgartigimod, and to trial procedures. Each event should be recorded separately in the eCRF.

All AEs spontaneously reported by the patient or reported in response to the open question from the trial personnel: “*Have you had any health problems since the previous visit or since you were last asked?*,” or revealed by observation will be collected and recorded in the eCRF. When collecting AEs, the recording of diagnoses is preferred (when possible) to recording a list of signs and symptoms. However, if a diagnosis is known and there are other signs or symptoms that are not generally part of the diagnosis, the diagnosis and each sign or symptom will be recorded separately.

Any SAE, including death due to any cause, which occurs during this trial after signature of the ICF, whether or not related to efgartigimod, must be reported immediately (within 24 hours of the trial site’s knowledge of the event). All SAEs will be recorded (within 24 hours) on the paper SAE Report Form and the AE form in the eCRF, the investigator or delegated site staff should check that all entered data are consistent. An alert email for the SAE report in the eCRF will then automatically be sent by email to the sponsor’s designated CRO safety mailbox via the electronic data capture (EDC) system. The paper SAE Report Form should be faxed or emailed to the sponsor’s designated CRO (see the [Safety Mailbox/Fax](#) details on the title page of this protocol).

The report will contain as much available information concerning the SAE to enable the sponsor (or an authorized representative) to file a report, which satisfies regulatory reporting requirements. These timelines apply to initial reports of SAEs and to all follow-up reports.

Criteria for documenting the relationship to efgartigimod, as well as severity, outcome, and action taken will be the same as those previously described.

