5. SAFETY ANALYSES

5.1 ADVERSE EVENTS

5.1.1 *Available data*

Adverse events (AEs) are coded into system organ classes and preferred terms using the MedDRA version 24.1 (SEP2021). AEs were graded using the National Cancer Institute (NCI) Common Terminology Criteria for Adverse Events (CTCAE) version 5.0. For each AE, start and stop date/times are collected as well as severity, a seriousness flag, treatment relatedness, relatedness to procedures, action taken towards the study drug and outcome.

5.1.2 *Derivation rules*

Based on their start date/time, AEs will be allocated to the analysis period during which they started. Each AE will therefore be reported in only one period. Periods are defined in section 2.2.1. In case the AE start date/time is incomplete or missing and the AE could consequently be allocated to more than one period, AE will be allocated to the first possible cycle unless the available parts of the AE start or stop date/time provide evidence the assessments did not occur during that period.

Event rates per patient years of follow-up (PYFU) will be defined as the number of events divided by the sum of follow-up time (i.e. duration of treatment phase) of all participants per treatment expressed in years.

A death case is defined as an AE with outcome ‘fatal’.

Adverse events of special interest will be defined using MedDRA SOC ‘Infections and infestations’.

Infusion-related reactions (IRR) will be defined as all AEs with a MedDRA preferred terms that are listed in either:

- MedDRA Hypersensitivity SMQ broad selection
- MedDRA Anaphylactic reaction SMQ broad selection
- MedDRA extravasation events (injections, infusions and implants) SMQ broad selection, excluding implants

AND occurring within 48 hours of an infusion, or within 2 days in case no AE start time is available.

An AE for which the study drug was discontinued is defined as an AE with action taken ‘drug withdrawn’.

Treatment-relatedness will be dichotomised as follows in tables:

- Treatment-related: related, probably related, possibly related or missing
- Not treatment-related: not related, unlikely related, not applicable

	
Statistical Analysis Plan
	

ARGX-113-1705
	
Final Analysis
	
Final 1.0 of 20SEP2022

AE onset and duration will be calculated as follows when start and stop dates are fully known

- AE onset day (vs. first administration)

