5.1.3 Presentation of results

Adverse events occurring in ITP0 will only be listed. AEs will be tabulated by AChR-Ab status and overall and within AChR-Ab status, by cycle and overall.

An overview table will show the number and percentage of patients with at least one event, the number of events and event rates per patient years of follow-up for the following:

- TEAEs
- Serious TEAEs
- Grade ≥ 3 TEAEs
- TEAEs of special interest
- IRR events
- Fatal TEAEs
- Treatment-related TEAEs according to the Principle Investigator
- Procedures-related TEAEs according to the Principle Investigator
- Serious treatment-related TEAEs
- TEAEs for which the study drug was discontinued

Summary tables by MedDRA system organ class and preferred term will show the number and percentage of patients with at least one event. The table of TEAEs will additionally show the number of events.

	
Statistical Analysis Plan
	

ARGX-113-1705
	
Final Analysis
	
Final 1.0 of 20SEP2022

Separate tables will be prepared for the following TEAEs:

- Serious TEAEs
- Non-serious TEAEs
- Grade ≥ 3 TEAEs
- IRR events
- Treatment-related TEAEs
- Procedures-related TEAEs
- Serious treatment-related TEAEs
- Serious IRR events
- TEAEs for which the study drug was discontinued

All AEs, including pre-treatment events will be listed.

COVID related events (events with preferred term COVID-19, COVID-19 pneumonia, suspected COVID-19 and coronavirus infection) will be listed. This listing will include all collected AE information and additionally the cycle, onset since first efgartigimod dose, onset since last efgartigimod dose before AE onset, last total IgG before AE onset, the last percent change in total IgG before AE onset and the time when that reported total IgG was taken compared to AE onset.

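### A positive COVID-19 test must be recorded as an AESI, but the SAP's COVID term list has no test-result term, and its AESI rule catches such an event only if its term belongs to the infections SOC

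*Protocol*

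**What the plan says.** The protocol describes an AESI in three ways.

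- Section 7.2.1.1 gives the general rule: "any infection will be considered AESI in this trial".
- Section 1.4 expresses it through the coding dictionary: "AEs in the Infections and Infestations SOC have been defined as AESIs".
- Appendix 8, in the guidance to sites on suspected COVID-19, ties it to a laboratory finding: "The investigator needs to document a positive COVID-19 test as an AESI". This is current text, and it is also printed inside Section 4.3.2. It sits under question 1, in the branch for patients who have symptoms.

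The SAP uses the dictionary form only. Section 5.1.2 states: "Adverse events of special interest will be defined using MedDRA SOC", naming Infections and infestations. Section 5.1.3 adds a listing of COVID-related events, restricted to "events with preferred term COVID-19, COVID-19 pneumonia, suspected COVID-19 and coronavirus infection". For each case that listing shows the cycle, the time since the first and the latest efgartigimod dose, the last total IgG before onset with its percent change, and when that IgG sample was taken relative to onset.

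SAP 6.1 declares no departure from the protocol.

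**The concern.** The protocol's trigger is a test result, whereas both SAP selection rules work on coded terms. The COVID list is closed and holds only diagnoses. It makes room for suspected COVID-19 but has no term for a positive test. If a site enters the event as Appendix 8 words it, and the coder assigns a test-result term, the SAP has no rule that brings the event back.

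Infection is the only AESI named in this trial, because the drug lowers IgG. The dedicated AESI outputs are one row of the overview table (patients, events and rate per patient-year) and listing 16.2.7.6. No AESI table by preferred term is planned. An event missing from these outputs can only make the count lower, and a reader of the AESI row would have no sign of it. The COVID listing is also the only output described in SAP 5.1.3 that places a case beside exposure and IgG, so a case absent from it loses that context.

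**Working it through.** The plan gives no figure to reproduce. The check follows one event through the stated rules.

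**Inputs**

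| Item | Source | Content |
|---|---|---|
| Trigger | Protocol Appendix 8 | Positive COVID-19 test in a symptomatic patient is an AESI |
| Recording habit | Protocol 7.2.1.2 | "the recording of diagnoses is preferred (when possible) to recording a list of signs and symptoms" |
| Test results in general | Protocol 7.2.1 | Not AEs unless clinically significant |
| AE data fields | SAP 5.1.1 | "For each AE, start and stop date/times are collected as well as severity, a seriousness flag, treatment relatedness, relatedness to procedures", then action taken and outcome; no AESI flag is mentioned |
| Dictionary | SAP 5.1.1 | MedDRA 24.1; no rule for coding a positive-test entry |
| AESI rule | SAP 5.1.2 | Infections SOC only |
| COVID rule | SAP 5.1.3 | Four diagnosis terms |

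**Case A: the event is recorded and coded as COVID-19.** The term is on the list of four, so the event enters listing 16.2.7.8. As an infection diagnosis it is the kind of event that the SOC rule is meant to catch. There is no gap.

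**Case B: the event is coded to a test-result term.**

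1. *COVID listing 16.2.7.8.* The term is not among the four, so the event is absent. This follows from the SAP text alone.
2. *AESI row of table 14.3.1.1 and listing 16.2.7.6.* The event is absent if the term lies outside the infections SOC and present if it lies inside. The documents do not settle which.
3. *Full AE listing 16.2.7.1.* The event is present for any patient in the safety analysis set, because all AEs are listed.
4. *All-TEAE table 14.3.1.2.* The event is present if treatment-emergent, under whatever SOC the term carries.

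**Size.** Let m be the number of positive tests documented as AESIs, k the number of those coded to a test-result term, and T the patient-years of follow-up. Let s = 1 if the term lies outside the infections SOC and s = 0 if it lies inside. For treatment-emergent events:

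- Shortfall in the COVID listing = k.
- Shortfall in AESI events = s × k, which is 0 or k.
- Shortfall in the AESI rate = s × k / T.
- Shortfall in patients with an AESI is at most s × k, since a patient with another coded infection is still counted.

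k runs from 0 (every site records the diagnosis) to m (none does). The documents give neither k nor m, so the shortfall cannot be narrowed beyond 0 to m.

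**The case against.** The strongest reply is that the SAP follows the protocol's own definition. Section 1.4 uses the same SOC, and Section 7.2.1.1 speaks of any infection. On that reading Appendix 8 only reminds sites that test-confirmed COVID-19 is a reportable infection, and the test is supporting evidence; 7.2.1.1 lists confirmatory procedures among the details to be collected for an AESI. The instruction covers symptomatic patients, for whom a COVID-19 diagnosis is the natural entry and 7.2.1.2 prefers diagnoses. Section 7.2.1 discourages reporting bare test results. Data review before lock (Protocol 9.4) could query such an entry.

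Most of this stands. It supports an infection-based AESI rule and suggests that k will be small. It does not close the gap. The preference for diagnoses applies when possible, and it contrasts them with signs and symptoms rather than with test results. Appendix 8 is the more specific instruction and names the test. Neither document says that a positive-test entry will be queried or coded to the diagnosis.

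A reader might go further and infer that every AESI recorded as a positive test falls out of both the COVID and the AESI outputs, so that infection incidence is biased downwards. The documents do not support that. Loss from the AESI outputs depends on a dictionary placement they do not give, and the number of such entries could be zero. Nor do they show that the SAP sets aside an investigator's AESI flag, because the AE fields it describes include none.

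**Conclusion.** The concern holds in a limited form. The SAP does not say how a positive COVID-19 test documented as an AESI is captured. One consequence is certain: an event coded to a test-result term is not in listing 16.2.7.8. A second is conditional: it is also missing from the AESI row of table 14.3.1.1 and from listing 16.2.7.6 if the term lies outside the infections SOC, which is an assumption here.

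Such events would be misclassified rather than lost, since they remain in the general AE outputs. In a single-arm trial analysed descriptively no test result or decision rule is affected. The point merits correction because two closed selection rules can miss an event the protocol names as an AESI, and the repair is trivial.

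**What to change.** - **SAP 5.1.2:** extend the AESI definition to the infections SOC plus AE terms for a positive SARS-CoV-2 or COVID-19 test.
- **SAP 5.1.3:** add the same terms to the selection for listing 16.2.7.8.
- **Alternative to both:** state that AE entries reporting a positive COVID-19 test are coded to the COVID-19 diagnosis.
- **Investigator's AESI designation:** use it as a further criterion only if the eCRF is confirmed to hold one. Protocol 7.2.1.1 describes extra eCRF questions for infections, but SAP 5.1.1 mentions no flag.

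The cost is one or two SAP lines and a slightly longer term list, with no new data. The AESI count may rise slightly.

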4.4. Early Discontinuation

The criteria for roll-over into this trial (see Section 4.3) are to be followed explicitly. If it is noted that a patient who does not meet 1 or more of the inclusion and/or meets 1 or more of the

exclusion criteria is inadvertently rolled over, the Medical Monitor at sponsor's designated CRO and the sponsor's Medical Director must be contacted immediately.

Early discontinuation from the trial is defined as the permanent cessation of further participation in the trial prior to its planned completion.

Patients **must** be discontinued early from the trial if:

- They withdraw their consent.
- The investigator, after discussion with the sponsor's Medical Director, deems it is in the patient's best interest.
- Patient is pregnant.
- Patient receives rescue therapy (Part A only).
- Patient develops an SAE that is likely to result in a life-threatening situation or pose a serious safety risk to the patient.
- Prohibited medication is taken (Part A only) (see Section 6.8.1).

Patients **might** discontinue early from the trial if:

- Patient has clinical evidence of bacterial, viral or fungal disease or any other significant disease which could confound the results of the trial or put the patient at undue risk. In this situation, decision on whether or not to discontinue patients early from trial will depend on the evaluation on a case-by-case basis. Patients who, after evaluation of the above situations are not discontinued from the trial, may have a temporary interruption from trial treatment (see Section 4.4.1).

For patients who discontinue early from trial, the assessments will depend on the visit at which it was decided that the patient had to discontinue (see Section 5.4, Figure 1, and Figure 2).

Patients who discontinue early from the trial within a treatment period should perform the planned assessments of the corresponding treatment period visit. These patients will not receive any further administration of efgartigimod during the trial and will return for the ED visit 1 month (30 ± 2 days) after the last dose administration. An unscheduled visit can be organized if deemed necessary by the investigator.

Patients who discontinue early from the trial between the last visit of a treatment period (TP_nV4 or TPE_nV4) and the next intertreatment period visit (ITP_nVn or $ITPE_nVn$) should perform the ED assessments 1 month (30 ± 2 days) after the last dose administration.

Patients who discontinue early from the trial at the ITP (Part A) or ITPE (Part B) visit should perform the ED assessments, instead of the ITP_nVn (Part A) or $ITPE_nVn$ (Part B) assessments.

Patients who discontinue early from the trial after the ITP (Part A) or ITPE (Part B) visit should perform the ED assessments.

Any patient prematurely discontinuing the trial during Part A should perform the EoA/ED assessments according to the General Schedule of Assessments for Part A (Table 1). Any patient prematurely discontinuing the trial during Part B should perform the EoS/ED assessments according to the General Schedule of Assessments for Part B (Table 2).

All patients are free to withdraw consent from participation in the trial at any time, for any reason, specified or unspecified, and without prejudice to further treatment. Prior to actual withdrawal of consent, an effort should be made to perform a final set of assessments as per the EoA/ED visit in the General Schedule of Assessments for Part A (Table 1) or the EoS/ED visit in the General Schedule of Assessments for Part B (Table 2). Investigators will make and document all efforts made to contact those patients who do not return for scheduled visits.

Before enrolling in ARGX-113-2002 from Part B, patients must first complete the early discontinuation (ED) visit assessments specified in Table 2. The previous efgartigimod IV dose must have been received at least 30 days before entry into ARGX-113-2002. Patients who enroll in ARGX-113-2002 will not return to ARGX-113-1705.

The reason for early discontinuation from the trial must be documented by the investigator on the appropriate page of the eCRF.

